7.1. Subject Disposition

The number of subjects who enroll in the study and the number and percentage of subjects who complete each assessment will be presented. The frequency and percentage of subjects who withdraw or discontinue from the study and the reason for withdrawal or discontinuation will be summarized. In addition, significant known protocol deviations will be noted for individual subjects.

7.2. Demographics and Baseline Characteristics

Descriptive statistics will be used to summarize demographic and baseline subject characteristics for age, sex, weight, body mass index, race, and ethnicity. For continuous variables, the mean, median, standard deviation (SD), minimum, and maximum values will be reported. For categorical (nominal) variables, the number and percentage of subjects (or observations) will be reported.

7.3. Pharmacodynamic Analyses

7.3.1 Peripheral Blood Eosinophils

Individual eosinophil versus time plots will be presented for each participant. For eosinophils, AUEC and maximum decrease from baseline will be calculated for each participant using all on treatment timepoints. Calculations will be performed using non-compartmental analysis packages available in a statistical software. The primary analysis with eosinophils will use pAUEC and maximum decrease from baseline; other derived AUEC measures may be calculated (AUEC calculation without baseline adjustment and with normalization to baseline [pAUEC]) to evaluate how derived PD metrics impact trial design. Baseline adjustments will be based on the average of multiple measurements (i.e., day -1 and day 0, time 0), when available. If only a one of these measures is available, it will be used without averaging in the baseline calculation. PD parameters of mepolizumab, reslizumab, and placebo groups will be listed and summarized using descriptive statistics (n, mean, SD, coefficient of variation, mean, SD, minimum, median, interquartile range, and maximum) for each treatment arm.

7.4. Pharmacokinetic Analyses

Individual serum concentration versus time plots for mepolizumab and reslizumab groups will be presented for each participant. AUC_{0-inf} and C_{max} will be calculated for each participant using all on treatment timepoints as part of the secondary analysis. In addition, the following PK parameters will be calculated for each individual as exploratory analyses: AUC_{0-t}, T_{max}, apparent clearance (CL/F), apparent volume of distribution (V/F), elimination rate (K_{el}), and terminal half-life (t_{1/2}) PK parameters will be calculated for each participant using all on treatment timepoints. All parameters will be summarized using descriptive statistics (n, geometric mean, coefficient of variation, minimum, median, interquartile range, and maximum) for each mepolizumab and reslizumab treatment arm.

Calculations will be performed using non-compartmental analysis packages available in a statistical software. Serum concentrations below the limits of quantification will be set to zero for the purpose of this analysis. Subjects with all samples below the limit of quantification will be excluded from PK summaries. AUC_{0-inf} , $t_{1/2}$, and K_{el} for subjects will only be included for subjects with 3 or more concentration values on the terminal portion of the pharmacokinetic curve and with an adjusted coefficient of determinations (R^2) greater than 0.80.

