2.2. Secondary Objectives

The secondary objectives of this study are:

- To determine the values and variability of PK and PD characteristics at four dose levels (i.e., low, intermediate low, intermediate high, and high doses) for mepolizumab and reslizumab.
- 2. Explore PK and PD relationships using appropriate models for mepolizumab and reslizumab.

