4.3. Exploratory Endpoints

- Additional pharmacokinetic parameters for mepolizumab and reslizumab, including time of maximum concentration (T_{max}), elimination rate constant (K_{el}), area under the curve from time 0 to end of study (AUC_{0-t}), half-life (t_{1/2}), apparent clearance (CL/F), and apparent volume of distribution (V/F).
- Time course profiles, maximum increase/decrease from baseline, and AUEC for plasma proteomics and small RNA transcriptomics (set of markers be determined)

5. Analysis Populations

- For all analyses, subjects will be analyzed according to the dose and treatment received, not the dose and treatment to which subjects were randomized.
- The PD population will include all subjects who receive study drug and have at least 1 estimable PD parameter after dosing. For baseline-adjusted analyses, subjects must also have at least one valid baseline sample between screening to dose administration on day 1. Subjects without a valid baseline sample will be excluded from PD assessments where the derived metric is baseline adjusted.
- The PK population will include all subjects who receive study drug and have at least 1 estimable PK parameter after dosing. Subjects with all samples below the lower limit of quantification will not be included in PK population summaries.
- The PK/PD population (exposure-response population) will include all subjects from the PK and PD populations, including subjects treated with placebo or subjects

- where all PK samples were below the lower limit of quantification. The PK/PD population will be used for the model-based exposure-response analysis.
- Subjects who discontinued from the study before their assigned end of study day (referred to as early termination subjects) will be excluded from pharmacokinetic and pharmacodynamic parameter summary calculations.
- The safety population will include all subjects who receive at least 1 dose of any of the study drugs.

6. Data Screening and Acceptance

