6.1. Handling of Missing and Incomplete Data

The following imputation of missing values will be done:

- Pharmacokinetic measurements below the quantification limits will be considered equal to zero for all analyses.
- Non-pharmacokinetic measurements (e.g., eosinophils) below the quantification limits will be considered equal to the lower limit of quantification for all analyses unless explicitly noted otherwise.
- Missing pharmacokinetic or pharmacodynamic data (e.g., skipped outpatient visit) will not be imputed.
- For baseline adjusted measures, samples from Day 1, time 0 will be used for calculating this derived metric. In cases where the Day 1, time 0 sample is missing or invalid, the sample collected at check-in (Day -1) will be used, followed by the screening sample. If none of these samples are available or valid, then no baseline value will be calculated for the subject.

7. General Statistical Considerations

All data will be presented in data listings. Data from subjects excluded from an analysis population will be presented in the data listings, but not included in the calculation of summary statistics. In addition, the reason for exclusion from an analysis population will be noted for individual subjects.

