7.5. PK/PD Analyses

The dose- and exposure-response relationship between baseline-adjusted AUEC for eosinophils and $\Delta Eosinophil_{dec, max}$ and mepolizumab and reslizumab will be explored graphically (separate assessments for both response measures). Based on these observations, model-based analyses using statistical software will be conducted separately for each drug with respect to each of the above-mentioned PD measures.

The model-based analysis will explore both dose and exposure (i.e., AUC_{0-inf}, referred to as AUC below) as the dependent variable. All dose levels for a drug, as well as placebo data, will be combined for the analysis. Model selection will be based on the initial graphical assessment and will be selected from one of the following structures – linear,

E_{max}, and sigmoidal E_{max}. Multiple models may be evaluated based on the initial graphical analysis, in which case model selection will be based on a combination of goodness of fit plots, parameter uncertainty (i.e., parameter confidence intervals including zero), and Akaike's information criterion (AIC). General representations for each of the model structures and parameterizations is shown below:

Dose-relationship

Linear: Response $\sim E_0 + \text{Slope * Dose}$

 E_{max} : Response ~ $E_0 + E_{\text{max,dose}} * Dose / (Dose + ED_{50})$

Sigmoidal E_{max} : Response $\sim E_0 + E_{max,dose} * Dose^{\gamma} / (Dose^{\gamma} + ED_{50}^{\gamma})$

Exposure-relationship

Linear: Response $\sim E_0 + \text{Slope * AUC}$

 E_{max} : Response ~ E_0 + $E_{\text{max,exp}}$ * AUC / (AUC + EC_{50})

Sigmoidal E_{max} : Response $\sim E_0 + E_{max,exp} * AUC^{\gamma} / (AUC^{\gamma} + EC_{50}^{\gamma})$

Model evaluation will include residual variability error term but will not include any random effects or covariate evaluation on fixed effect.

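### In the SAP 7.5 exposure-response model, dosed subjects with no quantifiable sample sit at placebo exposure, while dosed subjects who fail the terminal-phase rule have no exposure value

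*SAP*

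**What the plan says.** Four SAP rules meet here.

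- **Who has an AUC0-inf (7.4).** AUC0-inf, t1/2 and Kel "will only be included for subjects with 3 or more concentration values on the terminal portion of the pharmacokinetic curve", and whose adjusted R² is "greater than 0.80". Cmax and AUC0-t are not subject to this rule.
- **All-BLQ subjects in PK summaries (5 and 7.4).** "Subjects with all samples below the limit of quantification will be excluded from PK summaries"; Section 5 says the same of the PK population.
- **Who is in the exposure-response analysis (5).** The PK/PD population takes in everyone from the PK and PD populations, and names placebo subjects and subjects "where all PK samples were below the lower limit of quantification. The PK/PD population will be used for the model-based exposure-response analysis".
- **How BLQ is coded (6.1).** "Pharmacokinetic measurements below the quantification limits will be considered equal to zero for all analyses". Missing PK data are not imputed.

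On the models, SAP 7.5 states: "The model-based analysis will explore both dose and exposure". It defines exposure as AUC0-inf and pools all dose levels of a drug with placebo. Section 4.2 makes the exposure-response parameter estimates, AUC0-inf and Cmax secondary endpoints. No section states which AUC0-inf an all-BLQ dosed subject receives, or what the exposure model does with a dosed subject who fails the terminal-phase rule.

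**The concern.** Read together, the rules treat dosed subjects in the wrong order. The subject who carries some PK information drops out of the exposure model for want of a value. The subject who carries none stays in, at a value known to be too low. Zero is the true exposure for placebo. For a subject who received mepolizumab or reslizumab it is an artefact of the assay limit.

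If that subject's eosinophils fell, the model sees a drug response at zero exposure. It must raise E0 to accommodate it, and EC50 moves as a consequence. EC50 and E0 describe the lower part of the curve, which the low-dose arms are there to inform.

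A second, weaker question concerns the PK summaries. A secondary objective is "To determine the values and variability of PK and PD characteristics at four dose levels". With eight subjects per arm, an AUC0-inf summary that silently omits several of them may not represent the arm.

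**Working it through.** **No figure to reproduce.** SAP 3.2 states that there was no formal sample size calculation, and the documents give no LLOQ, half-life or PK variability. All sizes below are illustrative.

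**Step 1: follow three kinds of subject through the rules.**

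| Subject | In PK/PD population (5) | AUC0-inf available | Place in the 7.5 exposure model |
|---|---|---|---|
| Placebo | yes, named | 0 | AUC = 0, correct |
| Dosed, all samples BLQ | yes, named | only 0, through 6.1 | AUC = 0, with placebo |
| Dosed, some quantifiable, fails 7.4 rule | yes | none | cannot enter |

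**Step 2: effect of zero-coding on E0, by hand.** Assume true E0 = 0, Emax = 90, residual SD 15, eight placebo subjects and four active arms of eight, with EC50 at k times the typical low-dose AUC. A typical low-dose response is R = 90/(1 + k), which is 45, 30 or 18 for k = 1, 2 or 4. With m low-dose subjects moved to AUC = 0, the mean response there is mR/(8 + m). For k = 1 and m = 2 this is 2 × 45/10 = 9.

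**Step 3: the same by simulated Emax fits**, moving the m lowest-exposure low-dose subjects. Entries are medians.

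| k | m | E0 by hand | E0 fitted, zero-coded | EC50/true, full data | EC50/true, omitted | EC50/true, zero-coded |
|---|---|---|---|---|---|---|
| 1 | 2 | 9.0 | 6.8 | 0.97 | 0.98 | 1.17 |
| 1 | 4 | 15.0 | 12.7 | 0.98 | 0.97 | 1.33 |
| 1 | 8 | 22.5 | 23.0 | 1.00 | 1.01 | 1.78 |
| 2 | 2 | 6.0 | 4.7 | 1.01 | 1.01 | 1.19 |
| 2 | 4 | 10.0 | 8.2 | 1.06 | 1.02 | 1.33 |
| 2 | 8 | 15.0 | 14.8 | 1.00 | 0.99 | 1.59 |
| 4 | 2 | 3.6 | 2.7 | 1.05 | 1.06 | 1.19 |
| 4 | 4 | 6.0 | 4.5 | 1.00 | 1.00 | 1.30 |
| 4 | 8 | 9.0 | 8.8 | 1.03 | 1.03 | 1.66 |

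The hand figure is somewhat high for m = 2 and 4 because the lowest-exposure subjects respond less than the typical one. Further runs, some with other settings, put EC50 at 1.13-1.23 times truth for two subjects and 1.25-1.41 for four. Omission left it at about 0.97-1.07. Omission costs precision: with k = 1 and all eight low-dose subjects lost, the interquartile range of EC50 relative to truth widens from 0.49 to 0.62.

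**Step 4: the terminal-phase rule in the summaries.** Inputs are the SAP Attachment A sampling days to Day 63, which give 4 + 12 + 7 = 23 post-dose samples. Assumptions are a one-compartment model, half-life 10, 20 or 30 days, PK CV 40%, residual error 15% and, for SC dosing, absorption 0.3/day. Results are for the lowest dose.

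| Low-dose Cmax / LLOQ | Pass the rule | Geometric mean AUC, kept / all |
|---|---|---|
| 1 | 2-7% (18-30% all-BLQ) | 0.98-1.34 |
| 2 | 32-51% | 0.99-1.12 |
| 5 | 85-95% | 0.95-1.02 |
| 20 or more | 83-100% | 0.92-1.00 |

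The first row rests on very few kept subjects. Ratios below 1 arise with long half-lives. A slow decline over 63 days gives a poor R², so the rule then removes slow-clearance, high-exposure subjects.

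**Step 5: which common interval.** With half-life 20 days, ke = 0.693/20 = 0.0347/day. Take ka = 0.4/day. The share of AUC0-inf reached by t days after an SC dose is 1 − (ka·e^(−ke·t) − ke·e^(−ka·t))/(ka − ke). At Day 14 (t = 13) this is about 1 − 0.70 = 30%. At Day 63 (t = 62) it is about 1 − 0.13 = 87%.

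**The case against.** The strongest reply is that zero-coding is an inference. SAP 6.1 sets concentrations to zero, not AUC0-inf, and 7.4 may be meant to govern only the PK summaries. That is fair as a reading of intent. But 6.1 applies to all analyses, Section 5 deliberately keeps these subjects, and zero is the only value the written rules yield. If zero was not intended, the value is undefined, and the SAP still needs a sentence.

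A second reply is that all-BLQ subjects may never occur; a contingency clause is no evidence of expected frequency. This stands, and it is why the point is conditional.

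A third is that the plan already has protection. Each drug also gets a dose-response model that needs no AUC, the primary endpoints are eosinophil measures, and the summaries report n. This stands too and limits the consequence. It does not repair the exposure model, whose parameters are a secondary endpoint.

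A reader might go further and infer that the terminal-phase rule overstates low-dose exposure and distorts the lower curve. The documents do not support that. The rule selects on point count and fit, not on exposure, and Step 4 shows that its direction can reverse. Losing subjects by exposure costs precision but does not bias a correctly specified curve. Leaving all-BLQ subjects out of a geometric mean is also no error in itself, since it cannot take zeros; their number should simply be shown.

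**Conclusion.** The point holds for the exposure-response model, conditionally. If dosed all-BLQ subjects occur, the written rules place them with placebo and bias the fit. Two of eight low-dose subjects raise EC50 by roughly 13-23%, and E0 by about 3-7 points on a 90-point Emax; omitting them does not bias EC50. These sizes rest on an assumed Emax curve, an EC50 of one to four times the low-dose AUC, and an assumed residual SD.

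For the AUC0-inf summaries, the most that can be said is that they may be biased in either direction. In the simulation, loss is heavy only when the low-dose peak is within about twice the LLOQ, a figure the documents do not give. With a sensitive assay the effect is small, although long half-lives can still understate the mean by up to about 8%.

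Nor does the point call for replacing AUC0-inf as the main exposure. A partial AUC to Day 14 would capture only about 30% of it under the Step 5 assumptions. This is a change that should be made to the SAP text, not a flaw in the trial's primary analysis.

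**What to change.** 1. **SAP 5 and 7.5.** State that dosed all-BLQ subjects are not assigned AUC = 0. Omit them from the primary exposure-response fit, or treat their exposure as left-censored. Keep them in the dose-response fit, and show the exposure fit with AUC = 0 as a sensitivity analysis.
2. **SAP 7.5.** Keep AUC0-inf as the main exposure. Add a pre-specified sensitivity model using an AUC over an interval common to all arms, for example from dosing to Day 63, which needs no terminal slope. Subjects who fail the 7.4 rule then enter. Unmodified AUC0-t will not serve, because arms end at Day 63 or Day 123. All-BLQ subjects need the treatment in (1) here too.
3. **SAP 7.4.** Beside the AUC0-inf, t1/2 and Kel summaries, report for each arm the number all-BLQ and the number failing each terminal-phase criterion.

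The cost is SAP wording and a little programming, with no new samples or subjects. The primary exposure fit may lose a few subjects and some precision. The common-interval AUC misses part of the tail (about 13% under the Step 5 assumptions) and, with BLQ set to zero, runs somewhat low in low-exposure subjects, which is why it is proposed as a sensitivity analysis only.

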7.5. PK/PD Analyses

The dose- and exposure-response relationship between baseline-adjusted AUEC for eosinophils and $\Delta Eosinophil_{dec, max}$ and mepolizumab and reslizumab will be explored graphically (separate assessments for both response measures). Based on these observations, model-based analyses using statistical software will be conducted separately for each drug with respect to each of the above-mentioned PD measures.

The model-based analysis will explore both dose and exposure (i.e., AUC_{0-inf}, referred to as AUC below) as the dependent variable. All dose levels for a drug, as well as placebo data, will be combined for the analysis. Model selection will be based on the initial graphical assessment and will be selected from one of the following structures – linear,

E_{max}, and sigmoidal E_{max}. Multiple models may be evaluated based on the initial graphical analysis, in which case model selection will be based on a combination of goodness of fit plots, parameter uncertainty (i.e., parameter confidence intervals including zero), and Akaike's information criterion (AIC). General representations for each of the model structures and parameterizations is shown below:

Dose-relationship

Linear: Response $\sim E_0 + \text{Slope * Dose}$

 E_{max} : Response ~ $E_0 + E_{\text{max,dose}} * Dose / (Dose + ED_{50})$

Sigmoidal E_{max} : Response $\sim E_0 + E_{max,dose} * Dose^{\gamma} / (Dose^{\gamma} + ED_{50}^{\gamma})$

Exposure-relationship

Linear: Response $\sim E_0 + \text{Slope * AUC}$

 E_{max} : Response ~ E_0 + $E_{\text{max,exp}}$ * AUC / (AUC + EC_{50})

Sigmoidal E_{max} : Response $\sim E_0 + E_{max,exp} * AUC^{\gamma} / (AUC^{\gamma} + EC_{50}^{\gamma})$

Model evaluation will include residual variability error term but will not include any random effects or covariate evaluation on fixed effect.

7.6. Exploratory Omics Analysis

Various proteomics, transcriptomics, and genomic analyses may be performed on collected data for biomarker exploration. Additional details regarding the statistical methods for these analyses will be described in a separate plan.

7.7. Safety Analyses

7.7.1 Adverse Events

All AEs will be coded using the latest version of the Medical Dictionary for Regulatory Activities (MedDRA). The incidence of TEAEs, organized by system organ class and frequency, will be summarized by seriousness, severity, relationship to treatment, and by treatment at onset of the TEAE. A detailed listing of serious AEs and TEAEs leading to withdrawal will also be provided.

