2. Parameters (E_{max} , and EC_{50}) calculated by the model after combining data from low, intermediate low, intermediate high, and high doses of mepolizumab or reslizumab with placebo data.

Exploratory Endpoints

1. Plasma proteomics (differential expression of circulating proteins)

2. Plasma small RNA transcriptomics (differential expression of circulating small RNAs)

Study Design:

This is a pilot, randomized, placebo-controlled, single-dose, parallel arm study. Healthy subjects will be randomized to four dose groups (low, intermediate low, intermediate high, and high) of each drug (mepolizumab or reslizumab) or placebo.

Subjects will report to the study site for screening assessments from Days -21 to -2 and then will return to the site on Day -1 for baseline assessments. Prior to and following study drug or placebo administration on Day 1, they will undergo assessments as described in the Schedule of Events (Table 9-1). Subjects will stay in house for the first two weeks.

Depending on the treatment arm, subjects will return to the clinic a maximum of 9 times for PK and PD blood draws and additional study procedures as outlined in the Schedule of Events.

Subjects will be sampled daily for the first two weeks, weekly out to day 63 and half of the dosed subjects will be sampled monthly until day 123. Each treatment group should include equal representation of male and female subjects. For all scheduled outpatient visits (i.e., all visits after 2 weeks of in house residency, see Table 9-1), subjects will be required to return to the clinic within a four-hour window.

The planned cohort sizes and investigational product doses are as follows:

Subjects (n)	Treatment Group	Drug
8	A	Mepolizumab low (3 mg)
8	B	Mepolizumab low intermediate (6 mg)
8	C	Mepolizumab high intermediate (12 mg)
8	D	Mepolizumab high (24 mg)
8	E	Reslizumab low (0.1 mg/kg)
8	F	Reslizumab low intermediate (0.2 mg/kg)
8	G	Reslizumab high intermediate (0.4 mg/kg)
8	H	Reslizumab high (0.8 mg/kg)
8	I	Placebo

Subjects in groups A, B, E, and F will follow the Schedule of Events through day 63. Subjects in groups C, D, G, and H and placebos will follow the Schedule of Events through Day 123.

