5.1.2 Dosing Schedule

- Treatment Group A: Mepolizumab 3 mg, SC
- Treatment Group B: Mepolizumab 6 mg, SC
- Treatment Group C: Mepolizumab 12 mg, SC
- Treatment Group D: Mepolizumab 24 mg, SC
- Treatment Group E: Reslizumab 0.1 mg/kg, IV
- Treatment Group F: Reslizumab 0.2 mg/kg, IV
- Treatment Group G: Reslizumab 0.4 mg/kg, IV
- Treatment Group H: Reslizumab 0.8 mg/kg, IV
- Treatment Group I: Placebo, (4 subjects receive SC and 4 subjects receive IV)

Subjects in Groups A, B, E, and F will be discharged on Day 63, while all other subjects will be discharged on Day 123. If a subject discontinues from the study prematurely, all procedures scheduled for discharge Day (i.e., Day 63 or Day 123) will be performed.

Meal timing and components, activity levels, and general conditions in the study clinic will be as similar as possible on the treatment days.

Safety will be evaluated in terms of AEs, clinical laboratory results (hematology, serum chemistry, and urinalysis), vital sign measurements (blood pressure, heart rate, respiratory rate, and oral body temperature), safety 12-lead ECG results, and physical examination findings (see Table 9-1).

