5.7.4.1 Adverse Events

5.7.4.1.1 Adverse Event Definitions

An AE is defined as any untoward and/or unintended sign, including an abnormal clinical laboratory finding, symptom, or disease temporally associated with the use of a study drug, whether or not considered related to the study drug. Events or conditions that increase in frequency or severity during or as a consequence of use of a drug in human clinical trials will also be considered AEs.

A treatment-emergent adverse event (TEAE) is defined as an AE that begins after study drug administration.

An unexpected AE is any AE having a specificity or severity not consistent with the current investigator's brochure for the study drug(s).

A serious adverse event (SAE) is defined as any AE occurring at any dose that meets the following criteria:

- Results in death,
- Is life threatening,
- Requires hospitalization or prolongation of existing hospitalization,
- Results in persistent or significant disability or incapacity,
- Results in a congenital anomaly/birth defect due to exposure prior to conception or during pregnancy, or
- Is an important medical event that may not meet the previous criteria but, based upon appropriate medical judgment, jeopardizes the subject or requires medical or surgical intervention to prevent one of the outcomes listed previously.

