5.7.4.1.2 Adverse Event Reporting

The recording of AEs will begin after the subject signs the informed consent form and will continue until discharge (or early termination). All AEs, whether serious or nonserious and whether or not related to the study drug, must be recorded in the eCRF. Study subjects will be instructed to warn study staff if he or she has any unexpected symptoms. In addition, all subjects will receive a reminder telephone call approximately 24 hours before Check-in.

Any SAE (whether expected or unexpected) must be entered into the eCRF system and reported by facsimile to the medical monitor or designee using the SAE Reporting Form within 24 hours of the investigator or study clinic staff becoming aware of the event. It is the responsibility of the investigator to report all SAEs to the medical monitor, to provide the most complete report possible, and to assess each SAE for its relationship to the study drug. The investigator is responsible for obtaining follow-up information on all SAEs and submitting follow-up SAE data. Any unexpected SAEs must be reported promptly to the investigator's IRB as per the IRB's requirements.

In the event of a fatal or life-threatening SAE, the sponsor will notify the appropriate FDA authorities by telephone or facsimile within 7 calendar days of receipt of the report. The sponsor will follow all 7-day alert reports with a written report within 10 working days of receipt of the case. Serious AE cases that concern nonfatal, nonlife-threatening events that are unexpected and at least possibly related to the study drug will be submitted in writing to the FDA within 10 working days of receipt.

Furthermore, any AEs that are not expected, occur at a higher frequency, or would require modification of the study protocol and/or informed consent must be reported to the FDA within 10 working days.

Adverse events that are assessed by the investigator as possibly or probably related to the study drug will be followed until they resolve or stabilize. All SAEs will be followed until resolution.

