5.9.8 Safety Analyses

5.9.8.1 Adverse Events

All AEs will be coded using the latest version of the Medical Dictionary for Regulatory Activities. The incidence of TEAEs, organized by system organ class and frequency, will be summarized by seriousness, severity, relationship to treatment, and by treatment at onset of the TEAE. A detailed listing of serious AEs and TEAEs leading to withdrawal will also be provided.

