3.1. Study design

This is a randomized, double-blind, placebo-controlled, single-dose, parallel arm, pilot study. Healthy subjects will be randomized to one of four dose groups (low, intermediate low, intermediate high, and high) of each drug (mepolizumab and reslizumab) or placebo (Table 1). The study will be conducted at one center in the United States (Spaulding Clinical Research unit in West Bend, Wisconsin).

Subjects will report to the study site for screening assessments from days -21 to -2 and then will return to the site on day -1 for baseline assessments. Prior to and following study drug or placebo administration on day 0, they will undergo assessments as described in the Schedule of Events. Subjects will stay in house for the first two weeks and will return to the clinic for study procedures as identified in the Schedule of Events Depending on the treatment arm, subjects will return to the clinic up to 9 times for PK and PD blood draws and additional study procedures as outlined in the Schedule of Events.

All subjects will be sampled daily for the first two weeks and then weekly out to Day 63. Subjects in Groups C, D, G, H, and I will be sampled monthly until Study Day 123. Subjects in Groups A, B, E, and F will follow the Schedule of Events until Day 63 and all other subjects will follow the Schedule of Events until Day 123. Each treatment group should include equal representation of male and female subjects.

Table 1: Study Treatment Groups

Statistical Analysis Plan: SCR-006

Subjects (n)	Treatment Group	Drug
8	A	Mepolizumab low (3 mg)
8	В	Mepolizumab low intermediate (6 mg)
8	С	Mepolizumab high intermediate (12 mg)
8	D	Mepolizumab high (24 mg)
8	Е	Reslizumab low (0.1 mg/kg)
8	F	Reslizumab low intermediate (0.2 mg/kg)
8	G	Reslizumab high intermediate (0.4 mg/kg)
8	Н	Reslizumab high (0.8 mg/kg)
8	I	Placebo

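### TEAE incidence is tabulated by arm with no common time window, although lower-dose arms are followed to Day 63 and placebo and higher-dose arms to Day 123

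*SAP*

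**What the plan says.** - **What counts.** Protocol 5.7.4.1.1: "A treatment-emergent adverse event (TEAE) is defined as an AE that begins after study drug administration". The definition has an opening date and no closing date.
- **How long AEs are collected.** Under protocol 5.7.4.1.2, recording runs from consent to discharge or early termination.
- **When discharge occurs.** Protocol 5.1.2: "Subjects in Groups A, B, E, and F will be discharged on Day 63, while all other subjects will be discharged on Day 123". The synopsis places placebo in the longer group: "Subjects in groups C, D, G, and H and placebos will follow the Schedule of Events through Day 123". SAP 3.1 gives the same two schedules.
- **How TEAEs are summarised.** SAP 7.7.1 says their incidence "will be summarized by seriousness, severity, relationship to treatment, and by treatment at onset of the TEAE". Protocol 5.9.8.1 is worded the same way. Neither section gives a common cut-off, a split by onset period or a person-time denominator, and no other section supplies one.
- **Who is included.** The SAP section 5 safety population is everyone dosed, with no condition on length of follow-up.

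**The concern.** A by-arm incidence table invites comparison across its columns. Here the columns cover different lengths of time. Within each drug the two lower doses have the short window and the two higher doses the long one, so follow-up length is fully confounded with dose in a study built around dose-response.

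Two misreadings follow. With no drug effect, TEAE incidence can appear to rise with dose. The lower doses can also look safer than placebo, and a small real excess over placebo at those doses could be hidden. The phrase about treatment at onset does not help: each subject receives one dose, so it identifies the arm and sets no time limit.

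**Working it through.** **Inputs from the documents**
- Dosing on Day 1; last planned day 63 (A, B, E, F) or 123 (C, D, G, H, I).
- Nine arms of 8: 9 × 8 = 72 subjects. The four lower-dose arms hold 4 × 8 = 32.
- The plan states no TEAE rate, so it has no figure of its own to reproduce.

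**Unequal time at risk.** From Day 1 there are 63 − 1 = 62 days in the shorter arms and 123 − 1 = 122 in the longer ones. The ratio is 122/62 = 1.97. In the longer arms 60 of 122 days (49%) have no counterpart in the shorter arms.

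**Assumptions.** Incidence by Day 63 (p63) is set at 40%, 20% or 10%, the same in every arm (no drug effect). The hazard after Day 63 is r times the earlier hazard, with r = 1, 0.25, 0.10 or 0.

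**Incidence by Day 123:** p123 = 1 − (1 − p63)^(1 + 60r/62).

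Example with p63 = 0.40 and r = 1: 1 − 0.60^1.968 = 0.634. The gap per arm is 8 × (0.634 − 0.400) = 1.87 subjects.

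| p63 | r = 1 | r = 0.25 | r = 0.10 | r = 0 |
|---|---|---|---|---|
| 40% | 63.4% | 47.0% | 42.9% | 40% |
| 20% | 35.5% | 24.2% | 21.7% | 20% |
| 10% | 18.7% | 12.3% | 10.9% | 10% |

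The gap in expected affected subjects per arm of 8 is 8 × (p123 − p63):

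| p63 | r = 1 | r = 0.25 | r = 0.10 | r = 0 |
|---|---|---|---|---|
| 40% | 1.87 | 0.56 | 0.23 | 0 |
| 20% | 1.24 | 0.34 | 0.14 | 0 |
| 10% | 0.70 | 0.18 | 0.07 | 0 |

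**Chance of a misleading ordering.** Take X ~ Binomial(8, p63) for one lower-dose arm and Y ~ Binomial(8, p123) for placebo, independent. Each cell gives P(X < Y) / P(X > Y); with equal windows the two would be equal.

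| p63 | r = 1 | r = 0.25 | r = 0.10 | r = 0 |
|---|---|---|---|---|
| 40% | 76% / 11% | 51% / 30% | 45% / 36% | 40% / 40% |
| 20% | 67% / 16% | 46% / 30% | 41% / 34% | 37% / 37% |
| 10% | 55% / 19% | 39% / 28% | 35% / 31% | 32% / 32% |

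**Would a person-day rate solve it?** With no drug effect, the crude event rate per person-day in the longer arms relative to the shorter arms is (62 + 60r)/122. That is 1.00, 0.63, 0.56 and 0.51 for r = 1, 0.25, 0.10 and 0. It is unbiased only if the hazard is constant. If the hazard falls after Day 63, the bias reverses and the longer-followed arms look safer.

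**With a common window** to Day 63 every arm has 62 days at risk. Equal hazards then give equal expected incidence, whatever the value of r.

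**The case against.** The strongest reply is that no between-arm safety comparison is planned. TEAE incidence is only summarised, no AE test or trend is specified, and safety is not a primary or secondary endpoint. Each column correctly describes its own arm over its own follow-up, the SAP states the two schedules openly, and the data listings would let a reader rebuild a table to Day 63. Placebo against C, D, G and H is fair, as are A against B and E against F.

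The size is also assumed throughout. The 76% figure needs both the highest assumed rate and an unchanged late hazard. After one dose, with two weeks in house, weekly visits to Day 63 and then only Days 93 and 123, fewer late onsets are likely to be recorded, though the documents do not say how many. Arms of exactly 8 with complete follow-up are planned values; replacements and early terminations would alter them. A footnote giving follow-up by arm would also reduce misreading.

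These points limit the weight but do not remove the defect. The plan puts placebo and lower-dose incidences in one by-treatment summary, and neither the listings nor a footnote changes the numbers in it. The bias also has one direction, so pooling arms does not average it away.

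**Conclusion.** The concern holds. The unequal windows and the lack of any common cut-off come directly from the documents. As written, the summary is biased towards fewer TEAEs in A, B, E and F than in placebo or the higher doses, unless no event that would count starts after Day 63.

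The size rests on assumed rates. For 10% to 40% incidence by Day 63, the gap runs from 0 to 1.9 subjects per arm of 8. It is 0.6 or fewer if the late hazard is a quarter or less of the earlier one. No primary or secondary result changes, and the higher doses versus placebo are unaffected. This is a change that should be made because it costs almost nothing, not one on which the study depends.

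**What to change.** In SAP 7.7.1, state that the by-treatment TEAE table for all nine arms uses events with onset from dosing through Day 63. Add a separate table of TEAEs with onset on Days 64-123 for C, D, G, H and I. Apply the same wording to protocol 5.9.8.1 if it is next amended. Do not use a crude person-day rate in place of the common window, because it is fair only under a constant hazard.

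The cost is one sentence and one table split. No data are discarded and none need be added, since onset must already be known to classify an event as treatment-emergent.
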